**REVISION HISTORY**

Revision #	Version Date	Summary of Changes	Consent Change?
2	August 2021	Change BinaxNOW interval from 3 days to 5 days, add compensation, update details about data labeling and storage	Yes
3	September 2021	Add 50 participants with positive at-school BinaxNOW, add option to consent prior to initial BinaxNOW testing, clarify process for Spanish translation, change eligibility to include all MMSD staff and students ages 4-14 with at least one symptom who are getting at-school PCR testing, clarify criteria that define	Yes

PROTOCOL TITLE: SAFE AND HEALTHY SCHOOLS

		who will be excluded from the final study sample, add questions to data collection form	
4	October 2021	Add back-up data collection method, add questions to data collection form, update follow-up guidance for positive at-home BinaxNOW	
5	December 2021	Modify recruitment method to allow participants to directly contact or approach the study team, and also to allow the study team to gently approach potential participants; describe sharing of results for at-school antigen test; explain that all study participants will receive a BinaxNOW home testing kit, not just participants with negative at-school antigen tests	Yes
6	January 2022	Add option of study team collecting at-school BinaxNOW test if it isn't already being collected, change child age range to 4-19, and add lollipop-only alternative if study team runs out of BinaxNOW tests	Yes
7	April 2022	Add Accelerated Clinical Laboratories (ACL) as a lab service provider, in addition to Exact Sciences Laboratories.	Yes
8	May 2022	Change lollipop sample labels from coded to fully identifiable. Update recruitment to explain ACL introducing the study. Make lollipop-only an option if a potential participant is unwilling or unable to do at-home BinaxNOW testing. Extending study timelines—completing enrollment in August instead of March.	Yes

## 1.0 Study Summary

Study Title	Safe and Healthy Schools
Brief Summary	This study will target Madison Metropolitan School District school children ages 4-19 and staff who have not had a previous positive COVID-19 test within the past 3 months. It will enroll children and adults for 1-3 days to explore whether serial “at-home” BinaxNOW testing is feasible and non-inferior to “at school” single PCR testing for the evaluation of symptomatic individuals with a negative initial BinaxNOW. It will also explore whether lollipop swabs are more acceptable and perform as well as nasal swabs with PCR testing.
Number of study sites	1
Study Design	Community-based empirical research
Primary Objective	(1) Determine whether “at-home” BinaxNOW testing is feasible for families, (2) Evaluate whether serial “at-home” BinaxNOW testing is non-inferior to “at school” single PCR testing, (3) Compare the acceptability of lollipop swabs and nasal swabs, and (4) Compare the performance of lollipop swabs to nasal swabs with PCR-based testing.
Secondary Objective(s)	NA
Research Intervention(s)/ Investigational Agent(s)	NA
Drugs/devices used on study (including any IND/IDE #)	This study will evaluate the BinaxNOW COVID-19 Ag Card and the “lollipop” swab sample collection method
Study Population	Madison Metropolitan School District school children ages 4-19 and staff
Sample Size	400 with negative at-school BinaxNOW and 50 with positive at-school BinaxNOW. Total n=450.
Study Duration for individual participants	Up to 5 days
Study Specific Abbreviations/ Definitions	PCR: polymerase chain reaction EUA: emergency use authorization

## 2.0 Background

### 2.1 Relevant prior experience and gaps in current knowledge:

Current standards for COVID-19 diagnosis include nasopharyngeal (NP), nasal or saliva specimens to detect SARS-CoV-2 via polymerase chain reaction (PCR) test. Because NP swabs are cumbersome to perform, uncomfortable for the patient, require health providers in personal protective equipment, scare young children and are not practical for large groups or repeat testing, we have been exploring the use of “lollipop” swabs. A lollipop swab, is an oral swab, sucked on like a lollipop for 20 seconds. It is essentially a sample of saliva that is conveniently collected. A previous experience with the use of lollipop swabs for the detection of group A streptococcus in children with pharyngitis, prompted us to perform a pilot test to assess the sensitivity of the lollipop swab compared to a NP swab for the detection of SARS-CoV-2 in symptomatic individuals with PCR.

Additionally, our group has extensive experience training and implementing testing for SARS-CoV-2 in K-12 schools. During the 2020-2021 academic school year, we trained two elementary schools to perform SARS-CoV-2 reverse transcription-loop-mediated isothermal amplification (RT-LAMP) saliva-based testing in Madison, WI. More broadly, we visited more than a dozen schools and districts to train staff how to perform BinaxNOW antigen tests. We generated an online portal, complete with videos, training slides, and examples of consenting documents. Through these efforts, we provided more than 100 schools in Dane County with the tools needed to perform antigen tests in the spring of 2021.

### 2.2 Relevant preliminary data:

Our previous research showed that 25 symptomatic patients assessed within 7 days of onset of symptoms (and known to be infected with SARS-CoV-2) were all positive when a lollipop swab was used for collection. In addition, 5 asymptomatic patients known to be infected with SARS-CoV-2 also proved to be positive when evaluated with a lollipop swab.

### 2.3 Significance:

The prevalence of SARS-CoV-2 among school-aged children in the 2021-2022 academic year is unknown. Intense vaccination campaigns will reduce the number of cases, but vaccination uptake varies widely across Wisconsin. Children under the age of 12 years will likely not be eligible for vaccination until the late fall, leaving many children still susceptible to infection during part of the school year. With the large number of children simultaneously returning to school (with many extracurricular activities), and potentially decreased attention to mitigation

## PROTOCOL TITLE: SAFE AND HEALTHY SCHOOLS

strategies, there will be increased transmission of respiratory viruses among members of the school community.

We expect there will be a surge in respiratory illnesses caused by enterovirus, rhinovirus, community coronaviruses, influenza, RSV, parainfluenza, human metapneumovirus and adenovirus as well as SARS-CoV-2 in the fall and winter of next year. When schools reopened post COVID-19 shutdowns in Hong Kong and the UK, there were rapid increases in the cases of rhinovirus. This anticipated rise of symptomatic children requires a comprehensive strategy to quickly distinguish between cases of SARS-CoV-2 and non-SARS-CoV-2 infections and implement a policy to consistently enable a prompt return to school.

In order to appreciate the nuances of testing for infections with SARS-CoV-2, it is necessary to briefly discuss clinical presentation and viral replication.

**Clinical presentation and viral replication:** Since the beginning of the pandemic, it was recognized that children are infected with SARS-CoV-2 less often than adults and that their illness has been, in general, milder than in adults. Many children and adults are completely asymptomatic. However, when children are symptomatic, their symptoms take the form of a mild upper respiratory infection with nasal congestion, nasal discharge, sore throat or cough.

The time from when a person is exposed to the SARS-CoV-2 virus to the time that they become infectious to others is called the incubation period. Just before the onset of symptoms, virus multiplication in the nose and throat accelerates and the infected individual becomes infectious to others. Infectivity of a given individual peaks in about the next 24 hours. They remain infectious for about 5 days, during which time the amount of virus in the nose and throat gradually decreases.

**Diagnostic Testing for SARS-CoV-2 – Nucleic acid detection:**  
The gold standard for diagnostic testing has been detection of SARS-CoV-2 nucleic acids by a polymerase chain reaction (PCR). The first tests to be developed were performed on a sample obtained from the nasopharynx. Eventually, these PCR assays were modified to be performed on other samples including either nasal mucosal swabs or samples of saliva collected in small receptacles. The transition to the use of other samples has been important since acquiring the nasopharyngeal (NP) sample requires trained personnel and is uncomfortable for the patient. Repeated NP tests are dreaded.  
*Identifying the optimum sampling technique for children remains a challenge.*

## PROTOCOL TITLE: SAFE AND HEALTHY SCHOOLS

PCR tests are generally performed in hospital or commercial laboratories. They are expensive—usually costing \$75 to \$150 dollars. They also take time to perform; although some tests are run in as short a time as an hour or two; others take 6 to 12 hours. Transportation from the collection site to a centralized testing facility significantly prolongs turnaround time ranging from 1-3 days. These delays limit the use of PCR as a tool for infection control.

The PCR test will be negative during the incubation period because there is not enough virus present to give a positive reaction. Just as the individual is becoming symptomatic, the PCR becomes positive. As the titer of virus peaks during the next 24 to 48 hours, the PCR test stays positive and will remain positive for quite a few more days while the patient is symptomatic and infectious to others. Of importance, the PCR may even remain positive when the patient is no longer infectious to others, because the test detects the nucleic acids even though the virus is no longer capable of replication.

**Antigen testing:** Instead of detecting viral nucleic acids, the target for antigen tests is the nucleoprotein (N) protein of the SARS-CoV-2 virus. Antigen tests can be performed in a shorter time than PCR tests and are much less expensive. While antigen tests are less sensitive than PCR tests, they both detect individuals who are infectious. The Abbott company developed a very simple assay that has been commercialized for use both as point-of-care as well as an in-home test called the BinaxNOW-COVID-19 Antigen test (hereinafter call BinaxNOW). The test comes packaged within a card which is the size and shape of a credit card and which opens like a small book. In addition, there is a container of reagent. The reagent is delivered into a small hole in the card. A nasal swab is obtained from the patient by swirling the swab gently in the anterior nares several times. The swab is then inserted into the space where the reagent is located and turned several times. A positive test is indicated by the presence of 2 lines, very similar to home pregnancy tests. The testing time is 15 minutes. A positive swab can be detected within 5 to 8 minutes, but the test cannot be classified as negative until 15 minutes have elapsed. In addition, this test is CLIA-waived and can be performed by school health personnel in the school setting, eliminating the need for specimen transport and dramatically reducing turn-around-time and providing immediately actionable results for determining the need for exclusion from school.

The BinaxNOW test is reported to be approximately 94% sensitive in patients with symptomatic COVID-19 infections. Accordingly, it would be anticipated that if an individual who was truly infected with SARS-CoV-2 tested negative with the BinaxNOW test, then another test would almost certainly become positive if repeated within 24 hours, as the climb in viral load is particularly steep once

## PROTOCOL TITLE: SAFE AND HEALTHY SCHOOLS

symptoms have developed. On the other hand, if the symptomatic individual with a negative BinaxNOW test is not infected with SARS-CoV-2, the repeat BinaxNOW will be persistently negative.

**Testing in schools:** There are several instances in which testing individuals for SARS-CoV-2 infection in the school setting is useful. Children or teachers may arrive at school and suddenly notice symptoms, or they may become symptomatic during the day. For these scenarios, we want to determine if the individual is positive for SARS-CoV-2 so they can be isolated and contact tracing can be initiated. If the patient is not infected with SARS-CoV-2, then an individual will only need to remain at home until their symptoms have resolved.

BinaxNOW tests are a valuable adjunct to PCR testing in symptomatic individuals because they are available, simple, and rapid. A positive result for a student or staff member can rapidly exclude the individual from the class and begin contact tracing. However, Wisconsin Department of Health Services (DHS) requires that a negative BinaxNOW test in a symptomatic individual be followed by a PCR. This requirement reflects the imperfect sensitivity of the BinaxNOW card at 94% rather than 100%. However, PCR tests are inconvenient for families and time consuming, so many families prefer to be isolated for 10 days, creating a situation in which school will be missed unnecessarily. DHS is attempting to improve adherence to PCR follow-up testing by providing nasal swab kits directly to schools. However, transporting these swabs to the testing facility is time-consuming for staff, thereby adding cost and decreasing accessibility.

Given that mask use is likely to be less stringent in the future, the likelihood of an increase in community-acquired viral infections is very high. This will translate into a greater proportion of children and adults presenting with respiratory symptoms who will have a negative BinaxNOW because their infection is caused by a virus different from SARS-CoV-2. Accordingly, we need a less resource-intensive approach to test symptomatic individuals for SARS-CoV-2.

### 3.0 Study Objectives and Endpoints

3.1 **Aim 1:** We will test the hypothesis that serial at-home BinaxNOW testing will be feasible and non-inferior to the single at-school PCR testing program. To do this, we will distribute over-the-counter BinaxNOW antigen tests to volunteer families and create a protocol to ensure families can perform and report test results accurately to the school. We will address two key questions:

## PROTOCOL TITLE: SAFE AND HEALTHY SCHOOLS

1. Is ‘at-home’ BinaxNOW testing feasible for families?
2. Is serial ‘at-home’ BinaxNOW testing non-inferior to ‘at-school’ single PCR testing?

**Aim 2:** We will test the hypothesis that lollipop swabs are more acceptable to individuals and PCR testing is non-inferior to performing PCR on nasal swabs. To test this hypothesis, we will work with MMSD schools to incorporate a lollipop swab for PCR at the time a symptomatic student or staff receives a nasal swab for PCR that is part of the DHS program. We will address the following two key questions:

1. Are lollipop swabs more acceptable to individuals when compared to nasal swabs?
2. Will lollipop swabs perform as well as nasal swabs with PCR-based testing?

### 3.2 Hypotheses to be tested:

**Aim 1.1:** “At-home” BinaxNOW testing will be feasible for families.

**Aim 1.2:** Serial “at-home” BinaxNOW testing is non-inferior to “at school” single PCR testing.

**Aim 2.1:** Lollipop swabs are more acceptable to individuals than nasal swabs.

**Aim 2.2:** Lollipop swabs will perform as well as nasal swabs with PCR-based testing.

## 4.0 Number of Participants

### 4.1 Total number of participants to be accrued:

We expect to enroll approximately 450 participants.

### 4.2 Number of participants needed to complete the research procedures:

To achieve adequate statistical power, 358 participants with negative at-school BinaxNOW tests need to complete the research procedures, including the at-home BinaxNOW test.

An additional 50 participants with positive at-school BinaxNOW tests need to provide lollipop swabs.

### 4.3 Replacing enrolled participants:

If participants with negative at-school BinaxNOW test results do not complete the procedures within the target window, i.e., do not successfully completing the at-home BinaxNOW test within 72 hours, they will be replaced. We will continue enrolling until 358

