## PROTOCOL TITLE: SAFE AND HEALTHY SCHOOLS

participants have completed the research procedures within the target timeframe.

We will continue enrolling participants with positive at-school BinaxNOW test results until 50 participants have nasal and lollipop PCR results.

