### 5.2 Criteria that define who will be included in the final study sample:

For Aim 1, participants with a negative at-school BinaxNOW test and nasal PCR results who complete both the lollipop PCR and at-home BinaxNOW tests within 72 hours will be included in the final study sample.

Aim 2 will include participants who provide a lollipop swab that is successfully resulted at Exact Sciences or ACL.

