### 5.3 Criteria that define who will be excluded from the final study sample:

If certain samples do not provide a result—such as if samples are missing, compromised, or invalid—the subject will not be included in analyses for one or both of the study aims. Criteria for exclusion from analyses are as follows:

Aim 1

-Missing nasal PCR result

-Do not successfully complete an at-home BinaxNOW test within 72 hours of the at-school BinaxNOW test

Aim 2

-Missing nasal PCR result

-Missing lollipop PCR result

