### 20.3 Participant Population for Analysis:

For Aim 1, we will include all participants who complete the at-home BinaxNOW test within 72 hours (N=358) and have nasal PCR results. For Aim2, we will include all participants who have both nasal and lollipop PCR results.

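### Feasibility of at-home testing is a primary objective with no planned analysis, and the only formal Aim 1 population leaves out every family that did not complete the test within 72 hours

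*Combined protocol and SAP*

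**What the plan says.** - Section 1.0 puts first among the primary objectives whether at-home "BinaxNOW testing is feasible for families". Section 3.2 repeats it as hypothesis Aim 1.1. Section 3.1 adds that the study will "create a protocol to ensure families can perform and report test results accurately to the school".
- Section 4.3: if at-school-negative participants "do not successfully completing the at-home BinaxNOW test within 72 hours, they will be replaced". Enrolment goes on until 358 "participants have completed the research procedures within the target timeframe".
- Section 5.2: for Aim 1, at-school negatives with a nasal PCR result "who complete both the lollipop PCR and at-home BinaxNOW tests within 72 hours will be included in the final study sample".
- Section 5.3 lists as an Aim 1 exclusion "Do not successfully complete an at-home BinaxNOW test within 72 hours of the at-school BinaxNOW test".
- Section 20.3: "For Aim 1, we will include all participants who complete the at-home BinaxNOW test within 72 hours (N=358) and have nasal PCR results".
- Sections 20.1, 20.2 and 20.4 cover, for Aim 1, only negative predictive value (NPV), sensitivity, specificity, positive predictive value and non-inferiority. Section 20.6 adds a complete-case rule.
- Section 13.3 has the coordinator observe the test and verify the result. Once the result is recorded, the coordinator asks whether the family could have managed alone, what help was needed, and whether they could do it alone in future.
- Section 12.1 asks people who miss 72 hours to test as soon as possible, up to 5 days.
- Section 15.3 says that nasal and lollipop results from participants who fail to do the at-home test will still be used to explore Aim 1.

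**The concern.** A feasibility question is about the families who could not or did not manage the test as well as those who did. The plan fixes the number of successes at 358, so all the information on completion lies in how many people had to be asked. No section names that denominator. The one population stated for Aim 1 as a whole removes the failures, and the questionnaire items that bear on feasibility are put only to people who already have a result.

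One of four primary objectives therefore has no prespecified answer that counts unsuccessful families. The denominator could be chosen after the data are seen, and several choices are open:

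- 72 hours or 5 days;
- with or without replaced participants;
- with or without people who turn out to be unwilling or unable, whose participation section 13.3 calls complete after the lollipop swab.

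The conflict between section 15.3 and sections 5.3 and 20.3 adds doubt about who belongs to Aim 1.

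**Working it through.** **1. What N=358 is for.** Inputs (section 20.2): null NPV 91%, alternative 95%, one-sided alpha 0.05, power 90%. With an exact one-sample binomial test, 358 is the first N at which power reaches 90%: reject if at least 335 of 358 are true negatives, exact alpha 0.0487, power 0.909. The plan's figure is reproduced. It is sized for NPV and not for feasibility.

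**2. Completion in the section 20.3 set.** Everyone in the set completed within 72 hours, so the proportion is 358/358 = 100%. The Wilson lower limit is n/(n + z²) = 358/(358 + 3.84) = 98.9%. This holds whatever the true completion rate.

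**3. Completion with everyone asked as denominator.** The documents state no completion rate. Section 1.0 plans 400 at-school negatives and section 20.2 plans 400 kits, so 400 is an inferred denominator. Section 20.2 can also be read as 400 kits needed to find 358 initial negatives.

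For 358/400 = 0.895, the Wilson centre is (0.895 + 3.84/800)/(1 + 3.84/400) = 0.891. The half-width is 1.96 × √(0.895 × 0.105/400 + 3.84/(4 × 400²))/(1 + 3.84/400) = 0.030. The interval is 86.1% to 92.1%.

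| Asked (assumed) | 358/asked | Wilson 95% CI | Section 20.3 set |
|---|---|---|---|
| 375 | 95.5% | 92.9% to 97.2% | 100% |
| 400 | 89.5% | 86.1% to 92.1% | 100% |
| 450 | 79.6% | 75.6% to 83.0% | 100% |
| 500 | 71.6% | 67.5% to 75.4% | 100% |

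Only the 400 row has any link to the text. The others show the range.

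**4. The sections side by side.**
- 5.3 and 20.3 exclude from Aim 1 anyone without an at-home result within 72 hours. 15.3 uses the swab results of people with no at-home result for Aim 1. Both cannot stand as written.
- 5.2 also requires a lollipop PCR for Aim 1. 5.3 and 20.3 do not.
- 12.1 allows at-home tests between 72 hours and 5 days. Section 20 gives them no use.

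**5. Does leaving out non-completers matter for NPV?** This needs inputs that the documents do not give. Assume 400 initial negatives, 36 PCR-positive, a second test that detects 47% of those (chosen to give the 95% design value), and 42 non-completers of whom x are PCR-positive.
- All participants: 364/(364 + 0.53 × 36) = 364/383.08 = 95.0%.
- Completers: [364 − (42 − x)]/{[364 − (42 − x)] + 0.53(36 − x)}.
- x = 0: 322/341.08 = 94.4%, a shift of −0.6 points.
- x = 10.5 (25% of non-completers): 332.5/346.015 = 96.1%, a shift of +1.1 points.

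The standard error is about √(0.95 × 0.05/343) = 1.2 points. The shift is at most about one standard error in this range and can go either way.

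**6. Why an imputed NPV range is not a bound.** Take x = 10 with 14 false negatives among completers. Counting all 32 PCR-negative non-completers as at-home negative, and the 10 PCR-positives as false negatives, gives 364/(364 + 14 + 10) = 364/388 = 93.8% (exact one-sided p = 0.028 against 91%). Without the 32 assumed true negatives it is 332/(332 + 14 + 10) = 332/356 = 93.3% (p = 0.077). The lower end depends on the imputation rule.

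**The case against.** The strongest reply is that no section proposes to compute a completion rate in the section 20.3 set. That set serves accuracy measures, which need an at-home result. Feasibility in section 3.1 is about performing and reporting the test accurately, and section 13.3 collects data on that: observed technique, verified results, ability and help. Missing the 72-hour window may partly reflect retention for a supervised study visit.

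Much of this stands. A reader might infer that the trial will report 100% feasibility, and the documents do not say so. A reader might also infer that feasibility cannot be answered from the data. That is wrong too: enrolled non-completers stay identifiable and activity dates and times are recorded (section 13.4), so a proper rate can be computed. Completion is one component of feasibility, and the performance items belong beside it.

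The gap remains. Sections 5.2, 5.3 and 20.3 speak of Aim 1 without limiting it to accuracy. If only accuracy was meant, feasibility has no population at all. No section assigns the ability and help items to an analysis, and they cannot speak for families without a result.

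On section 15.3, nasal plus lollipop results are Aim 2 data, so naming Aim 1 may be a slip. That makes it an editorial matter, but the sections still conflict.

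A last tempting inference is that the completer-only NPV is materially biased. The documents give no inputs to show this. Section 20.6 prespecifies complete case with a reason. Nor can PCR-negative non-completers simply be counted as at-home negative. Section 2.3 expects persistent negatives in uninfected people, but section 21.1 allows for a negative PCR with a positive at-home test.

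**Conclusion.** The point holds for feasibility. Primary objective 1 has no endpoint, denominator or analysis, and the one formal Aim 1 population would return 100% completion whatever happened. On the inferred 400 asked, the difference is 100% against 89.5%; the true gap depends on a denominator that the plan does not state. The conflict of 15.3 with 5.3 and 20.3, and the extra lollipop requirement in 5.2, are certain on the text but editorial in weight.

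The NPV consequence is secondary: modest, of either sign, and resting wholly on assumed inputs. It does not call the primary NPV analysis into question. The plan should be changed before analysis, but the defect can be repaired from data the study already records.

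**What to change.** 1. State that the section 20.3 completer set applies to accuracy (Aim 1.2) only. For Aim 1.1, use as denominator all at-school-negative participants who consented to the at-home test and were asked to do it, including replaced participants and those who later prove unwilling or unable. Report the proportion with a valid result within 72 hours and, separately, within 5 days, each with a 95% CI. Say whether the 12-hour floor in section 12.1 applies. Report the observed-performance, ability and help items among completers alongside. Set a success level in advance or label the endpoint descriptive.
2. Report separately, where recorded, the number enrolled as Lollipop Only because unwilling or unable. Note that section 25.1 aside, section 5.1 says decliners are not tracked, so this count covers only those who accepted the alternative.
3. Reconcile 15.3 and 5.2 with 5.3 and 20.3.
4. Optional: tabulate nasal PCR positivity in completers and non-completers, and add a supportive NPV that includes the actual at-home results obtained between 72 hours and 5 days. Do not present as a bound any range that counts all PCR-negative non-completers as at-home negative.

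Cost: wording in the analysis section and a little more analysis. N stays 358, with no added participants or visits. If the reason for Lollipop Only is not already captured, recording it would need a new data field, and earlier additions to the form came through protocol revisions. The downside is a feasibility figure below 100%.
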